15.1.1 All Adverse Events

All AEs recorded during the course of the trial (ie, assessed from signature of informed consent until the end of the Follow-up/End of Trial visit) will be coded according to MedDRA latest version and assigned to a SOC and PT.

TEAEs will be summarized by severity, using MedDRA latest version preferred term as event category and MedDRA primary system organ class (SOC) body term as Body System category.

The severity of AEs is assessed by the investigator per the Qualitative Toxicity Scale, as follows:

Mild: The participant is aware of the event or symptom, but the event or symptom is

easily tolerated.

Moderate: The participant experiences sufficient discomfort to interfere with or reduce his or

her usual level of activity.

Severe: Significant impairment of functioning: the participant is unable to carry out his or

her usual activities.

TEAEs related to trial treatment are those events with relationship missing, unknown or related.

The following will be summarized in an overview table with the number and percentage of subjects (and the number of events).

- Any TEAE
- TEAEs of special interest
- Trial treatment (either MS treatment or microgynon) related TEAEs
- MS treatment related TEAEs
- Microgynon related TEAEs
- Any serious TEAEs
- Trial treatment (either MS treatment or microgynon) related serious TEAEs
- MS treatment related serious TEAEs

- Microgynon related serious TEAEs
- Any severe TEAE
- Trial treatment (either MS treatment or microgynon) related severe TEAE
- MS treatment related severe TEAE
- Microgynon related severe TEAE
- TEAEs leading to death
- Trial treatment (either MS treatment or microgynon) related TEAEs leading to death
- MS treatment related TEAEs leading to death
- Microgynon related TEAEs leading to death

TEAEs will be summarized in tables with:

- The number and percentage of subjects by treatment with at least one TEAE and the number of events overall and by SOC and PT. Group/SOC terms will be sorted alphabetically and PTs within each group/SOC term will be sorted by descending frequency.
- The number and percentage of subjects by treatment with at least one non-serious TEAE and the number of non-serious TEAE applying frequency threshold of 5%. Group/SOC terms will be sorted alphabetically and PTs within each group/SOC term will be sorted by descending frequency.

In addition, the following tables will be provided. Group/SOC terms will be sorted alphabetically and PTs within each group/SOC term will be sorted by descending frequency (based on all treatment groups combined):

- A table by severity of TEAEs with the number and percentage of subjects by treatment with at least one TEAE and the number of events by SOC and PT.
- A table by relationship to trial treatment (either MS treatment or microgynon) with the number and percentage of subjects by treatment with at least one TEAE and the number of events by SOC and PT.
- A table by relationship to MS treatment with the number and percentage of subjects by treatment with at least one TEAE and the number of events by SOC and PT.
- A table by relationship to microgynon with the number and percentage of subjects by treatment with at least one TEAE and the number of events by SOC and PT.

Pre-treatment AEs (AEs with onset after informed consent but before start of treatment) and TEAEs will be listed separately.

15.1.2 Adverse Events Leading to Treatment Discontinuation

TEAEs leading to permanent discontinuation of trial treatment will be summarized including number of subjects, percentage and number of events.

A listing of TEAEs leading to permanent discontinuation of a trial treatment will additionally be provided.

15.2 Deaths, Other Serious Adverse Events, and Other Significant Adverse Events

15.2.1 Deaths

All deaths as well as reason for death will be based on information from the "Report of Subject Death" CRFs.

Listing of deaths, if any, will be provided displaying date and cause of death (including TEAE leading to death and relatedness to trial treatment, when applicable), and date and time of treatment administration.

15.2.2 Serious Adverse Events

A summary table of SAEs, if any, by treatment and overall will be provided displaying the number and percentage of subjects by treatment with at least one SAE and the number of SAE overall and by system organ class and preferred term. Group/SOC terms and PTs within each group/SOC term will be sorted alphabetically.

Listing of SAEs, if any, will be provided in addition.

15.2.3 Other Significant Adverse Event

15.2.3.1 Adverse Events of Special Interest

AEs that were identified as AEs of special interest (see Appendix 4 of the clinical study protocol) will be presented in a separate data listing.

15.3 Clinical Laboratory Evaluation

The following treatment labels will be used in tables and listings:

- Screening: During the screening period
- Run-in Period: During run-in period

- Microgynon + Placebo or Microgynon + Cladribine: For the measurement on Day 8, Day 9 and Day 14
- Follow-up: During follow-up/end of study period

All laboratory data will be reported with SI units. Laboratory parameters will be listed by subject and time-point and summarized indicating the treatment at the respective time-point using descriptive statistics and Box and Whisker plot for absolute values and change from baseline over time by treatment sequence, period and treatment.

Laboratory values that are outside the normal range will also be flagged in the data listings, along with corresponding normal ranges. Clinically significant abnormalities/outliers as per the Toxicity Grading Scale for Healthy Adult and Adolescent Volunteers Enrolled in Preventive Vaccine Clinical Trials will additionally be listed separately. Clinically significant values will be defined as values with toxicity grading of grade 2 or higher.

'Baseline' refers to the last scheduled measurement before administration of cladribine or placebo on Day 9 of each period. I.e. 'baseline' for period 1 refers to assessments on Day 21 of the run-in period.

Shift tables for post-dose shift (Low, Normal, High, Missing) will also be presented. The shift tables will be presented for follow-up versus screening.

See Appendix 5 of the clinical study protocol for a table of the safety laboratory evaluations.

Safety laboratory values are separated into:

- Hematology
- Biochemistry
- Urinalysis
- Other tests

Descriptive statistics shift tables and box plots will be created only for hematology and biochemistry results.

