4.1 Overall Design

This is a randomized, double-blind, 2-period, 2-sequence crossover study with a 1 month Run-in-Period in pre-menopausal women with active relapsing multiple sclerosis (RMS) requiring a disease-modifying RMS treatment. The overall study design is shown in Section 1.2, Figure 1.

The study design will comprise a ≤ 21 -day Screening period followed by a Microgynon Run-in-Period, followed by 2 sequential treatment periods (Study Periods 1 and 2) of 28 days each.

In case the Screening period lasts > 21 days and ≤ 60 days due to a delayed menstrual cycle of the participant (Run-in Day 1), it is acceptable that the participant starts with a delayed Run-in-Period without having re-performed the Screening assessments (in order to minimize unnecessary investigational burden for the participant). In case of the requirement to re-assess one or more Screening laboratory value(s), the Screening period may be prolonged for up to 8 weeks after the last Screening laboratory assessment and it is acceptable that the participant starts with a delayed Run-in-Period without re-assessing the complete set of Screening laboratory assessments. In both cases, the participant does not need to sign a new Informed Consent Form (ICF).

In the Run-in-Period as well as during both treatment periods, Microgynon (1 tablet/day containing 30 μg ethinyl estradiol [EE] and 150 μg levonorgestrel [LNG]) will be administered for 21 days, followed by 7 days off-treatment. In Study Periods 1 and 2 Microgynon will continue to be administered together with randomized treatment sequences of a 5-day once-daily cladribine 10 mg tablet treatment (Day 9 to Day 13 of Study Period 1) followed by a 5-day once-daily matched placebo treatment (Day 9 to Day 13 of Study Period 2) or vice versa; i.e., participants will be randomized to 1 of 2 double-blind treatment sequences, either cladribine-placebo or placebo-cladribine. Additionally, matched placebo treatment (Day 15 to Day 19) will be given in order to protect the blind for the cladribine-placebo sequence, that will receive their second weekly dose of cladribine on Day 15 to Day 19 in Study Period 2. In turn, the placebo-cladribine sequence will receive the second weekly dose of cladribine after the End of Study Visit as part of standard medical care.

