Participants randomized to the treatment sequence placebo-cladribine, will receive their first 5-day cladribine treatment in Study Period 2 (Days 9 to 13), and will receive their second 5-day cladribine treatment between 28 to 35 days thereafter, which conforms to the approved cladribine posology. It is important to note, that this second cladribine treatment week will not be part of the study itself but provided as standard medical care of participants in the following month after end of the study (see Section 6.7).

Participants randomized to the treatment sequence cladribine-placebo, will receive their first 5-day cladribine treatment in Study Period 1 (Days 9 to 13). Since, according to the study design, they will have to receive Placebo treatment 4 weeks thereafter (i.e., Study Period 2, Days 9 to 13), their second 5-day cladribine treatment will have to be deferred by 6 days (i.e., Study Period 2, Days 15 to 19). Accordingly, participants will receive their second 5-day cladribine treatment 34 days after having received their first cladribine 5-day treatment in Study Period 1. This schedule will only marginally deviate from the approved cladribine posology. In view of the long-lasting duration of action of cladribine, this modest deferral of the second cladribine treatment week is unlikely to affect the overall efficacy of cladribine treatment.

The second cladribine treatment on Days 15 to 19 in Study Period 2 will not alter the primary study objectives, as the treatment is only initiated after all PK and  samples will have been taken on Day 14 with the last sampling in the morning of Day 15 (initiation of second cladribine treatment thereafter).

In order to also enable blinding of the Days 15 to 19 cladribine treatment in Study Period 2, all participants from both treatment sequences will receive placebo on Days 15 to 19 in Study Period 1, and participants randomized to the treatment sequence cladribine-placebo (Days 9 to 13) will receive cladribine on Days 15 to 19 in Study Period 2 as their second dose (see Section 1.2, Figure 1).

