8.2.4 Clinical Safety Laboratory Assessments

- Blood and urine samples will be collected for the clinical laboratory tests listed in Appendix 5, at the time points listed in the SoA (see Section 1.3). All samples should be clearly identified
- Additional tests may be performed at any time during the study, as determined necessary by the Investigator or required by local regulations
- The tests will be performed by the central laboratory with exception of the following tests done locally: Urine test for pregnancy and drug screening, QuantiFERON®-TB test
- The Sponsor must receive a list of the central laboratory normal ranges before shipment of study intervention(s). Any changes to the ranges during the study must be forwarded to the Sponsor or designated organization

- The Investigator must review each laboratory report, document their review, and record any clinically relevant changes occurring during the study in the AE section of the eCRF. The laboratory reports must be filed with the source documents
- Laboratory/analyte results that could potentially unblind the study will not be reported to investigative sites or other blinded personnel. Instead the medical monitor will review lymphocyte counts. Details are described in Section 6.9.
- Any abnormalities in any of the laboratory parameters will be judged by a physician individually in relation to the reference ranges from the laboratory. For all findings of clinical relevance, follow-up examinations will be carried out until the deviation returns to normal or the absence of pathological relevance can be confirmed
- For specific laboratory parameters such as lymphocyte count, however, that are reflecting a direct and long-lasting cladribine treatment effect, monitoring will follow the recommendations in the SmPC (Merck Serono Europe Ltd., 2017)
- In case of the requirement to re-assess one or more Screening laboratory value(s), the Screening period may be prolonged for up to 8 weeks after the last Screening laboratory assessment. From a participant safety perspective and in order to minimize unnecessary investigational burden for the participant it is acceptable that the participant starts with a delayed Run-in-Period of the study without re-assessing the complete set of Screening laboratory assessments. The participant does not need to sign a new ICF.

The laboratory parameters to be determined are provided in detail in [Appendix 5](#).

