9.4.2 Safety Analyses

Safety data analysis will be conducted on the Safety Analysis Set. The number and percentage of participants experiencing at least 1 TEAE will be summarized by treatment as well as the number of events. Tables by relationship to study drug and by severity will be generated. AEs will be coded using Medical Dictionary for Regulatory Activities terminology.

All laboratory data will be reported with SI units. Laboratory parameters will be summarized using descriptive statistics for absolute values and change from baseline over time, by postdose shifts relative to baseline, Box and Whisker plots plus and data listings of clinically significant abnormalities/outliers as per the Toxicity Grading Scale for Healthy Adult and Adolescent Volunteers Enrolled in Preventive Vaccine Clinical Trials/out of the normal range.

Vital signs and ECG data will be summarized by changes-from-baseline values by treatment and for each sequence group using descriptive statistics. Clinical noteworthy ECG findings for individual participants will be listed and summarized as appropriate.

The following are defined as clinical noteworthy (not limited to but including) QTcF categories:

- QTcF duration \geq 450, 470, and 500 ms;
- QTcF change from baseline \geq 30 and 60 ms

Endpoint	Statistical Analysis Methods
Primary	N/A
Secondary	For safety assessments and continuous measurements will be summarized by means of descriptive statistics (i.e., number and percentage of observations, number and percentage of missing observations, mean, standard deviation, median, 25th and 75th percentiles [Q1 and Q3], minimum, and maximum) and categorical data will be summarized by means of frequency tables (i.e., count and percentages), if not stated otherwise.
Tertiary/Exploratory	N/A

N/A=not applicable.

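### In the cladribine-placebo sequence the Period 2 laboratory baseline is a post-cladribine sample, so the Period 2 haematology change leaves out any fall over the preceding 28 days

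*SAP*

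**What the plan says.** **Laboratory baseline.** SAP 15.3 defines it period by period: it "refers to the last scheduled measurement before administration of cladribine or placebo on Day 9 of each period". For Period 1 the SAP names the sample: "baseline' for period 1 refers to assessments on Day 21 of the run-in period". For Period 2 the Schedule of Activities has haematology on Day 9, Day 14 and at End of Study.

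**Labels and summaries.** SAP 15.3 gives Day 9 and Day 14 values the treatment label of the current period, and gives follow-up a label of its own. Absolute values and changes are both summarised by sequence, period and treatment.

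**Persistence.** Protocol 8.2.4 singles out lymphocyte count as "reflecting a direct and long-lasting cladribine treatment effect". Protocol 6.9 and the Schedule of Activities mark Run-in Day 21 as the baseline.

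**Shift tables.** Protocol 9.4.2 plans to report laboratory data "by postdose shifts relative to baseline". SAP 15.3 instead states: "The shift tables will be presented for follow-up versus screening". SAP section 7 nevertheless says that the protocol's methods were adopted.

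**The concern.** Resetting the baseline in each crossover period suits a measurement that has returned to its starting level. By the protocol's own description, lymphocyte count may not have done so. In the placebo-cladribine sequence both period baselines precede any study cladribine. In the cladribine-placebo sequence only the Period 1 baseline does. The same column heading, change from baseline, therefore means different things in the two sequences.

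Change in safety laboratory tests is part of the secondary safety endpoint. In the cladribine-placebo sequence, a fall that developed between the first course and Period 2 Day 9 becomes the zero point. Further decline or recovery from there to Day 14 appears as a Microgynon + Placebo change. The shift tables do not fill the gap numerically: they are categorical, they cover follow-up only, and by follow-up both sequences have had cladribine.

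**Working it through.** **Inputs**
- Period length: "2 sequential treatment periods (Study Periods 1 and 2) of 28 days each" (Protocol 4.1).
- First course in the cladribine-placebo sequence: "5-day once-daily cladribine 10 mg tablet treatment (Day 9 to Day 13 of Study Period 1" (Protocol 4.1).
- Second course in that sequence: starts on Period 2 Day 15 (Protocol 4.2).
- End of Study: 4 to 7 days after Period 2 Day 21, that is Period 2 Day 25 to 28 (Protocol 4.1 and Schedule of Activities).

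**Formula.** Running day = (period − 1) × 28 + day. Period 1 Day 9 is running day 9, and the last dose of the first course is on running day 13.

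**Reproducing the plan's figure.** Protocol 4.2 says that "participants will receive their second 5-day cladribine treatment 34 days after having received their first cladribine 5-day treatment in Study Period 1". Period 2 Day 15 is 28 + 15 = 43, and 43 − 9 = 34 days. The figure is reproduced, so the calendar is right.

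**Timing in the cladribine-placebo sequence**

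| Sample | Running day | Days after first cladribine dose | Baseline used by SAP 15.3 |
|---|---|---|---|
| Run-in Day 21 | 21 − 28 = −7 | 16 days before | is the Period 1 baseline |
| Period 1 Day 14 | 14 | 14 − 9 = 5 | Run-in Day 21 |
| Period 2 Day 9 | 37 | 37 − 9 = 28 | is the Period 2 baseline |
| Period 2 Day 14 | 42 | 42 − 9 = 33 | Period 2 Day 9 |
| End of Study | 53 to 56 | 44 to 47 | not stated |

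Period 2 Day 9 is also 37 − 13 = 24 days after the last dose of the first course. End of Study is 53 − 43 = 10 to 56 − 43 = 13 days after the second course starts. In the placebo-cladribine sequence, Period 2 Day 9 is the first day of cladribine, so a pre-dose sample there is unexposed.

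This takes the Period 2 Day 9 sample as pre-dose. If it were missing or drawn after dosing, the preceding scheduled sample would be Period 1 Day 14, which also follows cladribine in this sequence.

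**What the reset removes.** Let f be the proportional fall from Run-in Day 21 to Period 2 Day 9, and g the further fall from there to End of Study. The change at Period 2 Day 9 is zero under the SAP rule and −f from run-in. If End of Study uses the Period 2 baseline, the share of the total fall that is shown is

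(1 − f)g / [1 − (1 − f)(1 − g)].

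The documents give neither f nor g, so the values below are assumptions, with a starting count of 1500 cells/mm³ and g = 10%.

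| f | Count at Period 2 Day 9 | Change from run-in at Period 2 Day 9 | Count at End of Study | End of Study change, Period 2 baseline | End of Study change, run-in baseline | Share shown |
|---|---|---|---|---|---|---|
| 10% | 1350 | −150 | 1215 | −135 | −285 | 47% |
| 30% | 1050 | −450 | 945 | −105 | −555 | 19% |
| 50% | 750 | −750 | 675 | −75 | −825 | 9% |

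The share does not depend on the starting count. With g = 30% it is 73%, 41% and 23%. With g = 0 it is zero.

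**The case against.** A reader might infer that the plan conceals the lymphocyte fall. The documents do not support that. SAP 15.3 also summarises and plots absolute values by sequence and period, so the Run-in Day 21, Period 1 and Period 2 levels can be compared. It lists every value by participant, flags values outside the normal range, and lists grade 2 or higher values separately. The follow-up shift starts from screening, before any study cladribine, and spans both courses in this sequence.

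A reader might also infer that detection of the adverse event of special interest is weakened. It is not. Protocol Appendix 4 defines it as Grade 3 or 4 lymphopenia, with no reference to change from baseline. The SAP counts and lists these events, and the Medical Monitor reviews white cell counts during the study.

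The period-specific baseline also has a proper use: it isolates within-period change. If Run-in Day 21 replaced it altogether, a fall caused by Period 1 cladribine would appear in rows labelled placebo. Safety is descriptive, with no test or decision rule.

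All of this stands, and it limits the point without removing it. Absolute group summaries do not give the spread or extremes of within-participant change, and threshold listings do not give the average effect. The screening shift misses falls within the normal range. A second-year participant may enter at 800 cells/mm³ (Inclusion Criterion 4), below the central laboratory lower limit of 1,000 to 1,200 given in Exclusion Criterion 19, and would then show Low to Low.

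**Conclusion.** The point holds as a gap in the change-from-baseline reporting of one of the two sequences. After Period 1 Day 14, five days after the first dose, no planned summary in the cladribine-placebo sequence gives numerical within-participant change from a value before study cladribine. The one possible exception is End of Study, where the SAP names no baseline. To claim that follow-up changes are understated would go beyond the text; what the documents show is an ambiguity.

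The timing of 28 and 24 days rests on the nominal calendar. The size of the omitted fall is unknown. Appendix 4 puts the largest proportion of Grade 3 or 4 cases 2 months after the first dose, later than the last scheduled sample at day 44 to 47, and gives no mean change at day 28. The percentages in the working are illustrations only.

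Separately, the shift-table reference in SAP 15.3 differs from Protocol 9.4.2, and SAP section 7 does not acknowledge it. The primary PK analysis is unaffected. This is a cheap improvement to a descriptive secondary endpoint.

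**What to change.** In SAP 15.3:

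1. Keep the period-specific change. For haematology, add change from Run-in Day 21 at every later visit, including Period 2 Day 9, Period 2 Day 14 and End of Study.
2. State which baseline End of Study changes use.
3. Mark Period 2 values in the cladribine-placebo sequence as post-cladribine, so that the placebo label is not read as unexposed.
4. Add shift tables, by sequence, from Run-in Day 21 to Day 14 of each period and to follow-up, in line with Protocol 9.4.2. Keep follow-up versus screening if wanted, and record it in SAP section 7 as a departure.

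The Run-in Day 21 sample is already scheduled, so no new data are needed. The cost is SAP wording and a few extra descriptive tables. In the Period 2 placebo rows of the cladribine-placebo sequence the added change will include the earlier cladribine effect, which is why the marking in item 3 should accompany it.

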1.3 Schedule of Activities

- The Schedule of Activities (SoA) is provided below.

Schedule of Activities – Screening, Run-in-Period and Study Period 1

Assessments & Procedures	Screening (up to 21 days before Day 1) ^b	Run-in- Period	Intervention Study Period 1 (Days)									Notes	
			D 1 to 28	D 8	D 9	D 10	D 11	D 12	D 13	D 14	D 15		D 21
Residency				X	X	X	X	X	X	X	X		In individual cases Investigator may allow participants to stay overnight at home from Day 8 to Day 12. In-patient stay is required from the evening of Day 13 until discharge on Day 15 after completion of all planned study assessments.
Ambulatory Visit	X	X										X	Run-in-Period: ambulatory visits on Days 7, 14 and 21
Written Informed Consent	X												Prior to any screening procedures
Inclusion and Exclusion Criteria review	X			X ^a									a Re-check before administration on: contraception method, blood loss and lifestyle considerations. Results of safety laboratory on Day 21 of Run-in-Period (Baseline).
Demographic Data	X												
Physical Examination	X												
Herpes Zoster Serology	X												Serology diagnosis, if ABS negative vaccination and at least 4 weeks before cladribine administration
Medical History / Concomitant Disease	X												
Prior and Concomitant Treatment	X	X	X	X	X	X	X	X	X	X	X	X	

Assessments & Procedures (cont'd, Study Period 1)	Screening (up to 21 days before Day 1) ^b	Run-in- Period D 1 to 28	Intervention Study Period 1 (Days)									Notes
			D 8	D 9	D 10	D 11	D 12	D 13	D 14	D 15	D 21	
Hematology, Clinical Chemistry & Urine Analysis	X	X								X		Run-in-Period on Day 21 (Baseline)
QuantiFERON®-TB Test	X											Done in local laboratory
Serum Pregnancy Test	X											
Urine Pregnancy Test		X	X									A negative urine pregnancy test must be in place at Day 7 of Run-in-Period and on Day 8 of Study Period 1.
Alcohol Breath Test / Drugs of Abuse	X		X									See Appendix 5 . On Day 8 urine drug screen is done locally
Height / Weight / Body Mass Index (BMI)	X	X									X	Additional weight control: Run-in-Period on Day 21 and on Day 21 Study Period 1
Vital Signs	X	X		X	X	X	X	X	X			Run-in-Period on Days 7, 14 and 21. Days 9-13 predose and 1 h postdose; on Day 14 at 24 h and 25.5 h postdose (Day 13) of cladribine/placebo administration
12-lead ECG	X			X						X		On Day 9 predose and 1.5 h postdose; on Day 14 at 24 h and 25.5 h postdose (Day 13) of cladribine/placebo administration
Randomization		X										Within 10 days after Run-in-Period Day 21

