Assessments & Procedures	Intervention Study Period 2 (Days)									End of Study	Notes
	D 8	D 9	D 10	D 11	D 12	D 13	D 14	D 15	D 21	4-7 days after completion of D21	
Residency	X	X	X	X	X	X	X	X			In individual cases Investigator may allow participants to stay overnight at home from Day 8 to Day 12. In-patient stay is required from the evening of Day 13 until discharge on Day 15 after completion of all planned study assessments.
Ambulatory Visit									X	X	
Physical Examination										X	
Prior and Concomitant Treatment Review	X	X	X	X	X	X	X	X	X	X	
Hematology, Clinical Chemistry & Urine Analysis		X					X			X	
Urine Pregnancy Test	X									X	A negative urine pregnancy test is required prior to cladribine administration on Day 9.
Alcohol Breath Test / Drugs of Abuse	X										See Appendix 5 Urine drug screen is done locally
Weight / BMI	X									X	
Vital Signs		X	X	X	X	X	X			X	On Days 9-13 predose and 1 h postdose; on Day 14 at 24 and 25.5 h postdose (Day 13) of cladribine/placebo administration
12-lead ECG		X					X			X	On Day 9 predose and 1.5 h postdose; on Day 14 at 24 h and 25.5 h postdose (Day 13) of cladribine/placebo administration
Participant Diary Collection										X	

Assessments & Procedures (cont'd, Study Period 2)	Intervention Study Period 2 (Days)									End of Study 4-7 days after completion of D21	Notes
	D 8	D 9	D 10	D 11	D 12	D 13	D 14	D 15	D 21		
Empty Microgynon Packing Collection										X	
Administration of Microgynon	Daily intake D1 to D21										Microgynon should be taken at the same time between 7:00 a.m. and 9:00 a.m.
Fasting (≥ 10 h before visit)		X	X	X	X	X					≥ 10 h before cladribine/ placebo administration and at least 1 h postdose
Standardized Meals / Beverages	X	X	X	X	X	X	X				
Administration of Cladribine / Placebo		X	X	X	X	X			X		Between 8:00 a.m. and 10:00 a.m. after overnight fasting. Participants will receive cladribine/placebo on Days 15-19 of Study Period 2 as well to keep the blinding.
PK Blood sampling EE and LNG						X	X	X			On Day 13 in the morning (predose of Microgynon administration); On Day 14 predose and at 0.5, 1, 2, 4, 6, 8, 12, and 24 h (D15) postdose
PK Blood Sampling Cladribine		X	X	X	X	X					On Day 9 predose of cladribine/placebo administration; on Days 10-13 predose and at 0.25, 0.5, 1, 1.5 and 2.0 h postdose of cladribine/placebo administration
CCI											
Adverse Events	X	X	X	X	X	X	X	X	X	X	

2 Introduction

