Participant's total duration of participation will be 3 cycles of hormonal contraceptive (84 days) plus the Screening period of up to 21 days and the End of Study Visit 4 - 7 days after Day 21 of the second period. Therefore, the total duration of treatment with hormonal contraception (HC) is 63 days (3 cycles of HC of 21 days), treatment duration with cladribine is 5 days for the sequence placebo-cladribine, and 10 days for sequence cladribine-placebo and the total duration of each participant in the study is 82 to 105 days.

A detailed schedule of study procedures/assessments is provided in Section 1.3.

CCI

The anticipated clinical duration of the study including a ≤ 1 month Screening phase, a 21 months recruitment phase and the 3 months treatment phase is a total of ≤ 25 months.

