ss=at steady state; AUC_T=Area under the concentration-time curve from zero to tau; C_{av}=average concentration; C_{min}=minimum observed concentration during a complete dosing interval; C_{trough}=concentration observed immediately before next dosing; DBP=diastolic blood pressure; ECG=electrocardiogram; EE=ethinyl estradiol; h=hour; LNG=levonorgestrel; CGI PK=pharmacokinetic; PTF%=peak-to-trough fluctuation; PR=pulse rate; QTc=corrected QT intervals; SBP=systolic blood pressure; t_{max}=time to reach the maximum observed concentration collected during a dosing interval; TEAEs=treatment-emergent adverse events.

6 Overview of Planned Analyses

All final, planned analyses identified in the Clinical Trial Protocol and in this IAP will be performed only after the last subject has completed the last visit, i.e. end of trial visit/early termination visit with all trial data in-house, all data queries resolved, and the database locked.

A blinded data review meeting will be held prior to database lock. In addition, no database can be locked until this IAP has been approved.

7 Changes to the Planned Analyses in the Clinical Trial Protocol

The statistical methods as described in the protocol were adopted.

8 Protocol Deviations and Analysis Sets

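### SAP 15.3 takes laboratory shifts from screening to follow-up, not from the baseline set in protocol 9.4.2 and in SAP 15.3 itself, so the shift tables contain no placebo comparison

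*SAP*

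**What the plan says.** Protocol 9.4.2 lists the laboratory summaries as absolute values, change from baseline, and shifts, the last described as "by postdose shifts relative to baseline". The protocol's Schedule of Activities labels the Run-in Day 21 laboratory sample as baseline. Inclusion criterion 4 and protocol 6.9 name Screening and Run-in Day 21 (Baseline) as two separate time points.

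SAP 15.3 defines laboratory baseline as the last scheduled value before the Day 9 dose of cladribine or placebo in each period, and adds: "I.e. 'baseline' for period 1 refers to assessments on Day 21 of the run-in period". It uses that baseline for descriptive statistics and box plots "for absolute values and change from baseline over time by treatment sequence, period and treatment". For the shift tables it then says: "The shift tables will be presented for follow-up versus screening". No other pair of visits is given. SAP 7, which should list departures from the protocol, says only: "The statistical methods as described in the protocol were adopted".

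**The concern.** There are two problems, and they differ in kind.

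The first is a contradiction. Screening is not baseline in this trial, because a month of Microgynon lies between screening and Period 1. A programmer who follows SAP 15.3 will not produce the table that protocol 9.4.2 describes, and SAP 7 gives no sign of this.

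The second is a consequence of the chosen visits. The protocol does not require laboratory shifts by treatment, so the lack of a treatment split is not itself a departure. But a table that starts before Microgynon and ends after cladribine in both sequences mixes the two drugs and makes no use of the randomised placebo control. Laboratory change is a named secondary safety endpoint, and the shift table is the only planned laboratory table that counts participants as Low, Normal or High. As planned, it cannot show whether a move to Low followed cladribine or placebo. By contrast, SAP 15.5 tabulates QTcF categories by sequence, period and treatment.

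**Working it through.** No sample size or power figure is in dispute. The check is a day count.

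**Inputs**
- Three 28-day cycles: run-in, Period 1, Period 2 (protocol 4.1).
- Cladribine on Period 1 Days 9-13 and Period 2 Days 15-19 in the cladribine-placebo sequence, and on Period 2 Days 9-13 in the placebo-cladribine sequence (protocol 4.1, 4.2).
- End of Study 4-7 days after Period 2 Day 21 (protocol 4.1).
- Period 2 laboratory samples on Day 9, Day 14 and End of Study (Schedule of Activities). SAP 15.3 attaches treatment labels to Days 9 and 14.

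**Study-day scale.** With Run-in Day 1 as study day 1, Period 1 Day d is 28 + d and Period 2 Day d is 56 + d.
- Run-in Day 21 = 21
- Period 1: Day 9 = 37, Day 13 = 41, Day 14 = 42
- Period 2: Day 9 = 65, Day 13 = 69, Day 14 = 70, Day 15 = 71, Day 19 = 75, Day 21 = 77
- End of Study = 77 + 4 to 77 + 7 = 81 to 84

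**Check against the plan's own figure.** Period 1 Day 9 to Period 2 Day 15 is 71 - 37 = 34 days, as stated in protocol 4.2.

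**Reference visit**
- Run-in Day 21 is 37 - 21 = 16 days before the first blinded dose.
- Run-in Day 1 is 37 - 1 = 36 days before that dose, and screening is earlier still: up to 21 + 36 = 57 days before it with the standard screening window, and up to 60 + 36 = 96 days with the extension for a delayed cycle.

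**Exposure at follow-up.** In protocol 4.1, "the total duration of treatment with hormonal contraception (HC) is 63 days", all of it after screening. Cladribine exposure is:

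| | Cladribine-placebo | Placebo-cladribine |
|---|---|---|
| Cladribine days before follow-up | 5 + 5 = 10 | 5 |
| Days since first cladribine dose | 81 - 37 = 44 to 84 - 37 = 47 | 81 - 65 = 16 to 84 - 65 = 19 |
| Days since last cladribine dose | 81 - 75 = 6 to 84 - 75 = 9 | 81 - 69 = 12 to 84 - 69 = 15 |

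The 10 and 5 days match protocol 4.1. The number of completers with placebo only at follow-up is 0. Splitting the table by sequence would compare 10 with 5 cladribine days at different times after dosing, not cladribine with placebo.

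**What the scheduled samples could show**
- Day 14 is 5 days after the first and 1 day after the last of the Day 9-13 doses (42 - 37 and 42 - 41 in Period 1), so it shows early change only. It does give each completer one shift after cladribine and one after placebo.
- In Period 2 of the cladribine-placebo sequence, the placebo Day 14 value is 70 - 37 = 33 days after the first cladribine dose. Protocol 8.2.4 calls the lymphocyte effect long-lasting, so only Period 1 gives a clean placebo contrast for such effects.
- The Period 2 Day 9 sample in the cladribine-placebo sequence is 65 - 37 = 28 days after the first and 65 - 41 = 24 days after the last cladribine dose. If it is drawn before dosing, the other sequence has then had placebo only.

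**The case against.** The strongest reply is that the choice of visits is defensible and the loss small.

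- **Whole-study exposure.** The secondary objective concerns co-administration, assessed from first treatment to last assessment, and SAP 15.1 starts treatment at the first intake of any study drug. Screening is the only scheduled laboratory value before any drug, and follow-up is the last. This is a good reason to keep the table as a supplement. It does not turn screening into the baseline that both documents define elsewhere.
- **Same starting category.** Inclusion criterion 4 requires first-year participants to have white cell, lymphocyte and neutrophil counts in the normal range at both Screening and Run-in Day 21. For them the starting category is Normal with either reference. This stands: for those counts, changing the reference matters only for second-year participants, who need just 800 lymphocytes per mm³ at both visits. It does not restore a placebo comparison, because that is lost through the end visit.
- **Information elsewhere.** SAP 15.3 keeps change from baseline by treatment, flags out-of-range values, and lists values of grade 2 or higher. Grade 3 or 4 lymphopenia is an adverse event of special interest, and the Medical Monitor reviews counts during the study. Protocol 7.2 requires 16 evaluable participants, about 8 per sequence if balanced, so individual shifts can be read from listings. This limits the harm, but means and listings are not a count by category and treatment.
- **Minimum remedy.** Changing the reference to baseline, or declaring the choice in SAP 7, would resolve the contradiction. That is correct. The table to Period 2 Day 9 is a useful addition that neither document requires.

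**Conclusion.** The point holds. SAP 15.3 contradicts protocol 9.4.2 and its own baseline definition, and SAP 7 does not declare the difference. Followed as written, the shift tables run from before Microgynon to after cladribine in both sequences, with no placebo-only completer at the end visit, and cannot separate cladribine from placebo.

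The impact is moderate. It touches one set of descriptive secondary safety tables. The four primary PK endpoints, the decision rule and participant monitoring are unaffected. The SAP should be corrected, but the trial's main conclusion does not depend on it.

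The day counts assume visits on schedule and 28-day cycles. A placebo-cladribine participant who left before Period 2 Day 9 could have a placebo-only early termination value, but that would be incidental and not a planned comparison. The Period 2 Day 9 contrast rests on that sample being pre-dose, which the schedule does not say.

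**What to change.** Replace the shift-table sentence in SAP 15.3 with:

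> Shift tables will be presented (a) from each period's baseline (Run-in Day 21 for Period 1; the last scheduled pre-dose value, Day 9, for Period 2) to Day 14 of the same period, by treatment within sequence and period; (b) from Run-in Day 21 to the Period 2 Day 9 pre-dose value, by sequence; (c) from Run-in Day 21 to follow-up, by sequence. Follow-up versus screening is supplementary.

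Add this caveat:

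> In the cladribine-placebo sequence the Period 2 baseline already follows cladribine. For lymphocytes and other long-lasting effects the interpretable comparison is cladribine versus placebo given in Period 1, that is, (a) for Period 1 and (b). Day 14 shows early change only.

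Confirm that the Period 2 Day 9 laboratory sample is drawn before dosing. If it is not, (b) and the Period 2 baseline in (a) need rewording. Table (b) is recommended but is not needed to resolve the contradiction.

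If follow-up versus screening stays as the only shift table, declare it in SAP 7 as a change from protocol 9.4.2 and give the reason.

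The cost is SAP wording and a few more descriptive tables. No new sample is needed and the primary PK analysis does not change.
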